There is immense potential for future therapists and patients to benefit from the results of this study; if the hypotheses are supported, there will be cause for substantial revamping of MHC systems to capitalize on matching patients to therapists who have an empirically demonstrable track record of strength in treating patients with similar presenting problems.

7. Procedures to Maintain Confidentiality

- a. Describe the procedures in place which protect the privacy of the subjects and maintain the confidentiality of the data, as required by the federal regulations, if applicable.**

Multiple steps will be taken to protect confidentiality. As mentioned, minimal paper forms (e.g., diagnostic summary forms) will be kept in a locked cabinet in the PI's locked Psychotherapy Research Lab. There will be no hard copy data collected at the PsychBC sites. Virtually all of the data collected in this study (including consent) will be through a secure, web-based platform using a tablet or computer. This method offers greater protection because it guards against human error and negates the need for long-term storage of paper forms. Digital recordings of diagnostic assessments will be stored in a secure, password protected website. The recordings themselves will be encrypted.

Only designated study personnel will have access to identifiable, study specific, private information about human subjects. When registering on the TOP system, as required by PsychBC's standard operating procedures, both patients and therapists are assigned a random number code that links all subsequent assessments and is separated from identifiable information. This random number code will function as each participant's study code and will be used to link participants' data. As noted, all therapist and patient data (outside of diagnostic assessment summaries and the TOP administrations) will be collected through a web-based platform. The assigned participant code will be used to link/aggregate information, so private information will not be requested after the baseline assessment/consent process. Only the PI and essential research staff will have access to the list that links identifiable information with the participant's study code. Any audio recordings will be encrypted and password protected. Only the Co-PIs will know this password and have the capacity to access the recordings. When it is time to analyze the recordings for reliability coding, designated, trained RAs will also have access to the recordings; however, they will not have access to additional identifiable information (only the information required to complete the analysis). For any data used for research and publication purposes, the confidentiality of participant information will be ensured.

b. If information derived from the study will be provided to a government agency, or any other person or group, describe to whom the information will be given and the nature of the information.

The PI is required to submit information (i.e., contractual "deliverables") on a regular basis to PCORI (the study sponsor), including IRB protocols, interim progress reports, advisory board meeting minutes, engagement plan updates, evidence of diagnostic criterion reliability from training cases, interim data reports, presentation abstracts and documentation of acceptance, manuscript copies, letters of endorsement from scientific and consumer groups, final data analysis summary, and final research report. Details on deliverables are available in the aforementioned (and attached and updated) milestone schedule. No PHI will be transmitted to PCORI.

c. Specify where and under what conditions study data will be kept, how specimens will be labeled and stored (if applicable), who has access to the data and specimens, and what will be available to whom.

As noted, minimal paper forms (e.g., diagnostic summary forms) will be kept in a locked cabinet in the PI's locked Psychotherapy Research Lab. There will be no hard copy research-only data collected at the PsycBC sites. Virtually all of the data collected in this study (including consent) will be through a secure, web-based platform using a tablet or computer. Digital recordings of diagnostic assessments will be stored in a password protected website, and securely deleted by the project contract's term date. Only the relevant members of the research team will have access to the participants' data and only the PI will have long-term access to identifiable information. As noted, all assessments will be linked with a participant code. Any records linking the code to the participant's name or voice recording will be kept in a separate locked file cabinet in the PI's office. These records will be destroyed 5 years after the contract term date.

8. Potential Conflict of Interest

- a. Do any of the involved investigators or their immediate family (as described below) have consulting arrangements, management responsibilities or equity holdings in the Sponsoring company, vendor(s), provider(s) of goods, or subcontractor(s)? Y**

- b. Do any investigators or their immediate family have any financial relationship with the Sponsoring company, including the receipt of honoraria, income, or stock/stock options as payment? N**

- c. Is any Investigator(s) a member of an advisory board with the Sponsoring company? N**

- d. Do any investigators receive gift funds from the Sponsoring company? N**

- e. Do any investigators or their immediate family have an ownership or royalty interest in any intellectual property utilized in this protocol? Y**

“Immediate family” means a spouse, dependent children as defined by the IRS, or a domestic partner. If one or more of the above relationships exist, please include a statement in the consent form to disclose this relationship. i.e., a paid consultant, a paid member of the Scientific Advisory Board, has stock or stock options, or receives payment for lectures given on behalf of the sponsor. The consent form should disclose what institution(s) or companies are involved in the study through funding, cooperative research, or by providing study drugs or equipment. If you answer yes to any of the questions above, please go to the policies for more information.

9. Informed Consent

You can add different Consent Forms, Alteration Forms, and Waivers. Provide consent process background information, in the table below, for each Consent Form(s), Alteration Form(s), and Waiver(s).

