of global distress, a measure of existential isolation, and a measure of interpersonal problems, all described below in the listing of relevant phase 2 attachments to this protocol) through a secure online platform linked to their typical TOP administration. Next, the trained research assistant (RA) will administer (on the same individual teleconference) the *M.I.N.I. 7.0.2 International Neuropsychiatric Interview* (described below in the listing of relevant phase 2 attachments to this protocol). Following PsycBC's standard intake process and this research-focused baseline consent/assessment session, patients will be randomized to condition and assigned to a provider based on the experimental parameters of that condition (i.e., scientific match vs. pragmatic match). For their involvement in the additional diagnostic assessments and the additional measures that they will complete during the active treatment phase, patients will be compensated with a \$50 Amazon gift card (on a prorated schedule for any missed assessments).

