After the full baseline assessment, patients will be randomly assigned to condition (scientifically informed matched vs. pragmatic match) with a participating PsycBC provider. The UMass PC will generate the randomization sequences using an online random generator. Within condition, patients will be assigned sequentially to the therapists until they reach their study quota of 6 patients. Patients in the match condition will be assigned to therapists who have a demonstrated strength (derived from the baseline period) in treating, at a minimum, the patient's highest self-reported distress domain on the TOP-CS. Beyond the minimal match on the most elevated TOP-CS domain, our match algorithm will attempt to match patients to therapists on as many TOP-CS dimensions as possible, ultimately providing PsycBC with at least several well-matched choices for assignment within the match condition. In order to preserve this level of choice, there will be natural variability in the number of well-matched domains (some patients matched only on the minimum 1 TOP-CS domain, others matched on 2 or more domains). The match variability across both conditions will allow us to measure degree of match dimensionally as a moderator variable of our main treatment effect. Therapists will also be unaware of their patient's treatment condition (double blind), and they will treat both matched and non-matched patients (i.e., they will be crossed over the two conditions to minimize administrative disruptions). In the low probability event that there is no therapist meeting minimal match criteria for a patient in the match condition, that patient will be removed from the primary study analyses (though will, of course, still be offered treatment-as-usual at the clinic) and replaced with the next patient where a match does exist. As described in our power analysis below, we are oversampling in order to account for these "dropouts," or removed data points.

In addition to the baseline assessments already described, patients will be assessed via online surveys at regular intervals during treatment (the secure ORI platform will email hyperlinks to these surveys with reminders to complete them at the appropriate time intervals; the UMass PC can also follow-up with phone calls if needed). These during-treatment assessments will include the TOP-CS and measures

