We predict that the scientific match group will outperform the no match group to a clinically significant degree on TOP outcomes, global symptomatology, and interpersonal problems. We also expect that the match group will be more effective in promoting alliance quality and fostering more positive patient perceptions of treatment credibility and outcome expectation, all of which are established correlates (and candidate mechanisms) of positive treatment outcomes. Finally, we expect there to be less patient dropout in the match condition, and higher patient treatment satisfaction. Secondarily, we will examine 4 potential moderators of the expected between-group treatment effects on the primary TOP outcomes: (a) patient race (as it may be that the match algorithm is particularly potent, and an important responsiveness tool, for historically understudied or underrepresented patients), (b) degree of match of therapist strengths to patient problems (rated dimensionally as a ratio given that therapists can be matched on more than just the minimum 1 domain, and the elimination of harmful matches for any distressed domain reported by the patient), (c) patient distress severity, and (d) complexity of patient presenting problem. Thus, we will test if matching is only, or particularly, effective under the conditions of a central patient characteristic, a multiple domain match, and/or for patients with the most severe or complex pathology. As noted, we will also assess therapists' self-perceived strengths on the TOP domains. We expect to replicate previous literature showing that therapists are poor judges of their own efficacy, tending to underestimate negative effects and overestimate positive effects with their patients (Lambert, 2011), which would further underscore the importance of a data-driven match process.

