For the primary 3-level hierarchical model assessing treatment condition effects at the patient level on linear change rates within patients, we used Raudenbush and Liu's (2001) formula as incorporated in the Optimal Design program to determine the minimum numbers of therapists and patients needed to detect a moderate effect of condition (standardized difference between change rates = .50). With a minimum of 6 measurements spaced over the maximum 16 treatment weeks and assuming 5 patients per therapist, an intra-class correlation of .15, and an alpha of .05, we will need a total of 44 therapists and 220 patients to achieve a power of .80 to detect moderate condition effects on linear change rates. Factoring a 20% dropout rate at the patient level, running our experiment on 264 patients (6 per therapist) should provide sufficient statistical power to detect group differences on our primary outcome variables.

To summarize, based on this power analysis, we will for phase 1 access a naturalistic baseline assessment of a minimum of 44 consenting therapists' performance across a minimum of 15 cases to determine their strengths in treating the risk-adjusted domains measured by the TOP. We will then recruit a minimum of 264 patients for the phase 2 trial, assigning patients to the same 44 therapists who participated in phase 1 (they will see 6 cases each during the trial).

b. Describe the subject population, including the age range, gender, ethnic background, and type of subjects (e.g. students, professors, subjects with learning disabilities, mental health disorders, etc.). Please incorporate specific inclusion/exclusion criteria (e.g. physical and psychological health, demographic information, or other unique characteristics).

Therapist participants: As noted, our target sample is 44 therapist participants (age range = 30-65 years) who will be social workers, psychologists, and licensed clinical counselors. Reflecting PsycBC's therapist pool demographics, we anticipate that our provider sample will break down as follows: approximately 70% will be female; 88% will be white/non-Hispanic, 3% Black, 2% Hispanic, 2% "Other/mixed," and 5% Asian. Based on these projections and our power analysis, our targeted/planned therapist enrollment is indicated in an attached Targeted/Planned Enrollment Table (Therapists).

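### Degree of match is planned as a moderator, but it is partly produced by the arm after randomisation, so the condition × match term cannot answer the multiple-domain question

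*Combined protocol and SAP*

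**What the plan says.** The version in force is the second revision of the protocol. In section 2a, Phase 2, the baseline assessment comes first, and then "patients will be randomized to condition and assigned to a provider based on the experimental parameters of that condition". In the match arm the therapist must be strong in the patient's most elevated TOP-CS domain. The algorithm then seeks as many further matched domains as it can, and the clinic chooses from a short list. In the pragmatic arm, assignment follows availability, convenience or self-reported specialty (section 1b). Section 2a adds: "The match variability across both conditions will allow us to measure degree of match dimensionally as a moderator variable of our main treatment effect".

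The hypotheses paragraph of section 2a lists four secondary moderators of the between-group effect on the TOP outcomes. One is "degree of match of therapist strengths to patient problems (rated dimensionally as a ratio"), with a harm element: "the elimination of harmful matches for any distressed domain reported by the patient". Severity and complexity are separate entries: "c) patient distress severity, and (d) complexity of patient presenting problem". The intended inference is stated: "we will test if matching is only, or particularly, effective under the conditions of a central patient characteristic, a multiple domain match".

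Section 4a describes only the primary model, "assessing treatment condition effects at the patient level on linear change rates within patients". The text gives no moderator equation, centring rule, covariate list, denominator for the ratio, match score fixed before assignment, or mediation framework. The contract proposal and research plan listed among the attachments were not available and may say more.

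**The concern.** A moderator should exist apart from the arm. Patients at the same level of it are then comparable between arms, and the arm × moderator term has a clear meaning. Realised match is different: it is what the intervention delivers. A match-arm patient and a control patient with the same score reached it by different routes. One got there through an algorithm limited by a complex profile, the other through a lucky pragmatic assignment. What varies within an arm (short-list choice, availability, the patient's own profile) is not randomised either.

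At stake is the answer to the stated question of whether one matched domain is enough or several are needed. A null product term could be read as showing that degree of match is irrelevant. A negative one could be read as matching working less well with more domains, and a false one as moderation where matching does nothing.

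**Working it through.** **Inputs from the documents.** Standardised difference .50, "assuming 5 patients per therapist, an intra-class correlation of .15", alpha .05, 44 therapists, 220 patients, power .80 (section 4a). Quota of 6 per therapist and 12 TOP-CS domains (section 2a). Usable patients: 281 × .75 = 210.75, taken as 211 (third contract modification).

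**Assumed, because the documents give no value.** 1–7 elevated domains per patient; a 20, 33 or 50% chance that a therapist is strong in a domain; two-sided tests; no harm element; one change score per patient, with higher meaning better.

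**The plan's own figure.** None is given for the moderator model. For the primary effect, the design effect is 1 + (5 − 1) × .15 = 1.6 and the noncentrality is .50 / √(4 × 1.6 / 220) = 2.93. Power is .83 (normal) or .82 (t, 42 df), close to the stated .80. This variant treats therapists as nested in arms, although the plan crosses them. No match term enters.

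**Model examined.** Y = β0 + β1·arm + β2·match + β3·arm×match + error, by OLS.

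**Step 1: the score is the dose, and linear.** Let Y = b·match with b = .50 / (m1 − m0), where m1 and m0 are the assumed mean scores in the match and control arms. Then β1 = β3 = 0 by construction. With 220 patients and 1,500 runs per row:

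| m1 / m0 | b | estimated β2 | arm coefficient, no match terms | arm coefficient, full model | β3 significant |
|---|---|---|---|---|---|
| .45 / .35 | 5.00 | 5.00 | .50 | −.005 | 4.5% |
| .60 / .30 | 1.67 | 1.65 | .50 | .008 | 5.3% |
| .70 / .30 | 1.25 | 1.25 | .50 | .008 | 5.4% |

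The signal moves to β2, which is not randomised. If half the effect runs through match, the arm coefficient is about .25. If none does and nothing confounds match, it stays at .50.

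**Step 2: the dose levels off.** The set-up is the same, but benefit is flat above the midpoint of m1 and m0. The arm still does nothing beyond match, yet β3 is −1.8 to −2.1 and significant in 68, 75 and 64% of runs. Match-arm patients sit further up the curve, where it is flatter. Match was drawn here without reference to complexity, so adjusting for complexity would not remove this.

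**Step 3: the score is not the dose.** A patient with one elevated domain, matched, has ratio 1.0 and count 1. A patient with six elevated domains, three of them matched, has ratio .5 and count 3, so the order reverses. The next runs had 44 therapists, quota 6, N = 211, a .50 SD arm effect wholly through matching, and 600 trials per setting:

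| True benefit follows | Scored as | β3 significant |
|---|---|---|
| the score itself | same | 3–7% |
| count | ratio | 49–72% |
| ratio | count | 35–59% |
| ratio, capped at .5 | ratio | 31–86% |
| two or more matched domains only | ratio | 37–83% |

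A second check of the count-as-ratio, plateau and two-domain cases gave significant negative terms in 34–87% of trials, with arm coefficients of .13–.42. The last row matters most: benefit requires a multiple-domain match, yet the product term tends to be negative.

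**Step 4: no matching effect, but complexity is related to change.** Take the score as matched / elevated domains. Suppose the match arm secures only the top domain and is at chance elsewhere. With k elevated domains and strength probability p, the expected ratio is [1 + (k − 1)p] / k in the match arm and p in control. For p = .33:

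- k = 1: 1.00 against .33
- k = 3: (1 + .66) / 3 = .55 against .33
- k = 7: (1 + 1.98) / 7 = .43 against .33

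The ratio marks low complexity in the match arm but not in control. For complexity–outcome r = 0, −.1, −.2 and −.3, false interactions arise in 5–6, 7–8, 14–17 and 22–30% of trials (N = 211). Adding number of elevated domains and its arm interaction brings this to about 4–6%. A fixed 12-domain denominator also keeps the interaction near 5% (4–7%). At r = −.3, however, the dose term was then falsely significant in 29–60% of trials, so that denominator does not rescue an unadjusted model.

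**The case against.** The strongest reply is that the criticised equation is not in the plan. No formula is shown, the unseen attachments may contain one, and nothing says that the multiple-domain question rests on the product term alone. In step 1 the dose term would usually be significant, so an analyst would see the signal. This stands in part: the signal would be visible, but it is observational, and nothing in the text labels it so.

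The sizes rest on assumptions. That stands too. The documents give no dose-response, no r and no distribution of match. The harm element, missing data and repeated measures were not simulated, so the rates are indicative. Step 4 disappears with an ordinary covariate, and complexity is already a planned moderator. But it is listed separately, and the text does not say that it enters this model.

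Two stronger readings are tempting. A reader might infer that the arm largely determines match. The assignment rules show only that it contributes. In one check the arm explained 21–44% of the variance of the ratio and 9–33% of that of the count; in another it explained 10–24% of score variance. The plan itself expects variation in both conditions. A reader might also infer that the planned test would usually report no moderation, whatever the score. That holds only in step 1; steps 2 and 3 give the opposite result.

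**Conclusion.** The point holds in limited form. Realised match is a post-randomisation feature of the intervention, and its product with condition does not answer the question the plan asks of it. That much follows from the order of randomisation and assignment and needs no simulation. The direction of error cannot be settled from the documents: about 5% significance despite a real gradient if the score is the linear dose; often significant and negative (about 30–87%) under a mismatch, plateau or threshold; about 22–30% false positives if the ratio is matched / elevated domains and r = −.3.

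A reader might infer that the trial's main result is compromised. The documents do not support that. The primary model in section 4a tests condition without a match term, and nothing says that the arm coefficient of a moderator model would be reported as the treatment effect. This is a low-priority correction to one of four secondary moderators.

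**What to change.** 1. In section 2a, remove realised degree of match from the moderator list and from the sentence on match variability. Fix its numerator, denominator and harm element before analysis. Analyse it as a mediator or as-received dose, labelled non-randomised, adjusted for number of elevated domains (with its arm interaction) and baseline severity, and allow a non-linear dose. Do not base the multiple-domain conclusion on the condition × match term. This needs wording and baseline TOP-CS data already collected. The cost is that the degree-of-match result becomes openly observational.

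2. Optional, not required: if a true moderator is wanted, use a match score fixed before assignment and computed the same way in both arms, such as the best match attainable from therapists with open slots. It answers a different question, namely who has a good match available. It also needs availability data that the documents do not say are kept. Power is modest: in illustrative runs, attainable gain over the expected pragmatic match detected the interaction in 21–28% of trials when the score was a count. Attainable scores detected a benefit confined to two or more domains in only 4–7% with a ratio score. Those runs excluded patients without an available match from both arms, whereas the plan removes them from the match arm only, so these rates are rough.

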Importantly, at the time of this proposed IRB revision, most PsycBC clinicians who will choose to participate in the study will already have baseline data on the minimum 15 adult cases (through the patient's actual termination point or 16 weeks, whichever comes sooner) to establish their track record. In these cases, we simply need to enroll the therapist in the study (as discussed next). For therapists who wish to participate, but have yet to accumulate baseline performance data on the minimum 15 cases, we will track their performance (as per the TOP) on new, consecutive referrals until 15 total cases have been established for which the patient has either terminated or has been seen for at least 16 weeks. Few therapists will fall in this second category, and even if they do, they will generally only need a few cases to reach 15. Thus, we expect no issues completing the phase 1 performance baseline and finalizing the match algorithm for the phase 2 RCT by the established contractual milestone of 10/1/17.

Our minimum target therapist sample is 44 PsycBC providers (all of whom will be over the age of 18 themselves, and treating patients within the age range of 18-65). Therapists will be psychologists, clinical counselors, and social workers. Recruitment will be coordinated among our UMass-employed project coordinator (PC), the PsycBC-employed PC, clinic staff members, and the Co-PIs. Specifically, the PsycBC team will verbally present information about the study (both phases 1 and 2) to their providers during staff meetings. Alternatively, this information can be presented through email. At this preliminary recruitment stage, this information will be used to heighten awareness about the study and to garner interest in participating. (The verbal script for staff meetings and the email text are included as phase 1 attachments to this protocol.) The PsycBC PC will then provide the UMass PC (via

email) the names of providers who expressed interest in learning more about the study.

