Therapist Perceived Strengths (TPS). This measure was developed by the research team to assess therapists' beliefs about their effectiveness in treating the various TOP domains when uninformed of their data-driven TOP track record. This measure will allow us to examine how accurate therapists are in perceiving their own strengths and weaknesses.

Phase 2: At this phase, the RCT will commence. The therapists will have already consented prior to phase 1 to be involved in the entire study, and they will know that patient data from their naturalistic baseline cases will have been used to create a personalized performance report card that will inform a prospective match with new patients they will treat in the trial. The therapists themselves will not see their report cards (as they will have been informed at the time of consent); rather, this information will be used by the research team with regard to the match manipulation.

Phase 2 marks the beginning of *patient* recruitment into the RCT. The patient population will be adult men and women (age 18-70) in PsycBC's referral stream (largely Cleveland clinic and primary care [PCP] practice). Recruitment to the study simply means a willingness to be randomized to condition based on TOP-derived presenting problem and to complete supplemental assessments (for monetary compensation, as per below) at baseline, at regular intervals during treatment, and at posttreatment. As this is an effectiveness design with a premium on ecological validity and scalability, virtually all patients in the PsycBC network will be eligible. It is most likely that the sample will be predominated by the following problem domains: depression, panic, substance abuse, and poor quality of life. The only study-related patient-level exclusion criterion will be patients who are not the primary, informed decision-maker for their care. Thus, patients will present with a multitude of presenting problems across a spectrum of *Diagnostic and Statistical*

Manual of Mental Disorders (5th ed.; *DSM-5*⁴⁸) diagnoses. Our minimum study target sample size is 264 patients (6 per therapist).

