We do not anticipate problems meeting our recruitment numbers in the project time frame, as PsycBC schedules approximately 950 new patients per month. Moreover, their care model already uses the TOP to screen patients for appropriate level of care, and, as a formal subcontract on the project, they are willing to use a patient-level-best-matched clinician list that is generated in real time (based on the predictive validity of our match algorithm). Including the randomization protocol into the treatment delivery model will not create any systemic barriers.

Patients will flow into PsycBC via electronic or self-referrals. At initial contact, the PsycBC PC will ask patients for permission to be contacted by study personnel (i.e., the UMass PC) if they are interested in learning more about participation (this verbal script remains included as a phase 2 attachment to this protocol). If they are, they will be asked by the PsycBC PC to sign an authorization agreement (included in the phase 2 consent form) to allow their contact information (name, email address, and phone number) to be shared with the research team. The PsycBC PC's role is restricted to this recruitment task and administration of authorization to release the limited PHI; thus, no PsycBC personnel will be engaged in human subjects' research.

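### Unmatchable patients are removed and replaced after randomisation in the match arm only, so the analysed arms differ in matchability whenever the rule is used

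*Combined protocol and SAP*

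**What the plan says.** The governing text is section 2a (Study Procedures, Phase 2) of the 2nd protocol revision. Part C of the combined document describes that revision as final for most of the study. The same rule appears in section 2a of the original protocol and of the 1st revision.

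- **Order of events.** "After the full baseline assessment, patients will be randomly assigned to condition". The baseline TOP-CS is therefore known before allocation.
- **Criterion.** A match patient must go to a therapist with a demonstrated strength in at least the patient's most elevated TOP-CS domain.
- **Removal and replacement.** If there is "no therapist meeting minimal match criteria for a patient in the match condition, that patient will be removed from the primary study analyses" and "replaced with the next patient where a match does exist". The event is called low probability; no rate or cap is given.
- **Allowance.** "As described in our power analysis below, we are oversampling in order to account for these" removed cases, which the plan groups with dropouts.
- **Quota, in a separate sentence.** Within condition, "patients will be assigned sequentially to the therapists until they reach their study quota of 6 patients".
- **Pool.** "Our minimum target therapist sample is 44 PsycBC providers" (section 2a, Phase 1). The minimum patient target is 264, at 6 per therapist.
- **Controls.** No check, removal or replacement on matchability is stated for the pragmatic arm. Degree of match is measured in both arms, but only as a moderator.
- **Tooling.** The clinic works from a "patient-level-best-matched clinician list that is generated in real time".

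**The concern.** Randomisation makes the two arms alike in matchability. A filter applied afterwards to one arm undoes that. The filter depends on the patient's worst baseline domain and, on one reading, on which therapists still have room when the patient enrols. Either may be related to the rate of change, so the primary contrast would mix the effect of matching with a difference in case mix.

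Oversampling restores the number of patients, not their comparability. Replacements do not help either, because they are selected for being matchable.

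The plan also does not say whether the replacement takes the next random allocation or fills the vacated match place. In the second case that patient would not have been randomised at all.

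**Working it through.** **1. The plan's own precision.** Section 4a gives effect 0.50, ICC 0.15, 5 patients per therapist, 44 therapists, 220 patients, alpha 0.05 and power 0.80. As a rough check:

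- design effect = 1 + (5 − 1) × 0.15 = 1.6
- noncentrality = 0.5 × √(220 / (4 × 1.6)) = 2.93
- two-sided power on 42 df = 0.817, close to the stated 0.80

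The slope variance components are not given, so the named formula cannot be rerun exactly. For what follows I take the standard error implied by the stated power: 0.50 / (1.960 + 0.842) = 0.1785.

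**2. Bias formula.** Let q be the unmatchable share. Let D be the gap in outcome, in SD of change rate, between unmatchable and matchable patients under usual assignment. Controls include a share q of unmatchable patients and the match arm includes none, so |bias| = q × D. Type I error = P(|Z + qD/0.1785| > 1.96). Neither q nor D is in the documents; I show D = 0.2 and 0.5 as assumptions.

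**3. q if the criterion is therapist strength only (literal wording).** Section 3a says 82% to 96% of clinicians are above average in some area. Assume 12 independent domains. The chance of strength in any one domain is then 1 − 0.18^(1/12) = 0.133 or 1 − 0.04^(1/12) = 0.235. The chance that none of 44 therapists is strong in a given domain is:

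- 0.18^(44/12) = 0.19%
- 0.04^(44/12) = 0.0007%

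**4. q if a therapist at quota no longer counts.** At the stated minimums, 44 × 6 = 264 places for 264 patients. I simulated 300 trials per setting with 1:1 allocation. Controls go to the least-loaded open therapist, match patients to the least-loaded open therapist strong in their top domain, and removed patients use no place. There is one shared pool. Mean q at 96% and 82% prevalence of strength:

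| Pool | Domains equally common | 80% of patients in the four domains section 2a names as predominant (share assumed) |
|---|---|---|
| 44 therapists | 1.8% and 4.9% | 3.2% and 13.4% |
| 60 therapists | 0 to 0.2% | 0 to 2.7% |

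Independently coded repeats agreed to within about half a percentage point. With 44 therapists and equal domains, removals come late: at most about 0.5% in the first half of enrolment, against 7% to 18% in the last quarter.

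**5. Consequence.** Removals assume 132 patients per arm.

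| q | Match-arm removals (132q) | Bias at D = 0.5 | Type I error, D = 0.5 | Type I error, D = 0.2 |
|---|---|---|---|---|
| 0.2% | 0.3 | 0.001 | 5.0% | 5.0% |
| 1.8% | 2.4 | 0.009 | 5.03% | 5.0% |
| 4.9% | 6.5 | 0.025 | 5.22% | 5.03% |
| 13.4% | 17.7 | 0.067 | 6.6% | 5.3% |

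**The case against.** The strongest reply is that the event will hardly ever happen. The minimal criterion is defined by demonstrated strength, and the quota is a different sentence. Nothing says a full therapist stops meeting the criterion. On that reading q is about 0.2% or less and the sponsor's description of the event is fair. This stands, and it sets the lower end of the range. It does not make the rule symmetric, and the plan should say which reading applies.

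A reader might infer from 264 places for 264 patients that matches must run out. The documents do not establish this. Both figures are minimums, and Part C describes keeping further therapists under review for possible recruitment. Part D later raises enrolment to 281, above 264 places, without saying whether therapists were added or the quota moved.

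A reader might also infer much higher removal rates from the mention of multiple treatment sites, by supposing that patients could use only local therapists. Assignment to site-specific therapists is in the original protocol only. The current text drops it and gives neither the number of sites nor a site restriction, so I make no such estimate.

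Finally, the exclusion is from the primary analyses, and other analyses are not ruled out. No separate analysis plan is reproduced, and attachments such as the participant flow are listed but not shown. What can be said is that the available text describes no analysis that restores the removed patients or filters the controls.

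**Conclusion.** The flaw in the rule is certain; its size is conditional. Whenever the rule is used, the primary comparison is no longer between randomised groups. If the criterion means strength only, the effect is negligible. If quota counts, type I error at D = 0.5 is about 5.0% to 6.6%. The upper end needs exactly 44 therapists, the lowest prevalence of strength and a concentrated mix of domains, all at once. D = 0.5 is itself a gap as large as the planned effect.

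A reader might infer that the rule favours matching. The documents do not support that: the sign depends on whether unmatchable patients do better or worse under usual assignment, which is not stated. The point should be fixed because the remedy is cheap and because, without a count of removals, nobody can tell which case applied.

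**What to change.** 1. **Patients not yet randomised.** Run the match algorithm on the baseline TOP-CS before allocation. Randomise only patients with at least one qualifying therapist, log the others as not randomised, and delete the remove-and-replace rule. The TOP-CS is already complete by then and the list is produced in real time, so one existing step moves earlier. Screening rises by a factor 1/(1 − q): 264/0.96 = 275 patients at q = 4%. Parts C and D are written largely in the past tense, so this may reach few patients or none.

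2. **Patients already randomised.** Report the number removed. Define matchable identically in both arms from baseline TOP-CS and report cards, and state whether quota counts. If it does, open places can be reconstructed from assignment dates. Replace the one-sided exclusion with a symmetric comparison: either matchable patients in both arms, or all randomised patients as assigned where outcome data exist. Report the other as a sensitivity analysis. Follow-up of removed patients is not promised. Routine TOP data may exist, since the clinic collects the TOP as standard; report how many patients have none.
   - *Matchable set:* a share q of controls is lost, so the SE grows by √((1 + 1/(1 − q))/2). Power goes from 80% to 79.6% at q = 2% and 79.2% at 4%. Conclusions apply to matchable patients only.
   - *All as assigned:* if unmatched patients gain nothing, the effect is diluted to (1 − q) × 0.50, that is 0.49 at 2% and 0.48 at 4%, with power about 78% and 77%.

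3. **Replacements.** State how each was allocated. Report any patient placed in the match arm without a random draw and leave that patient out of the randomised comparison.
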